EPI	echo-planar imaging
FTND	Fagerström Test for Nicotine Dependence
KD	Ketogenic Diet

MPQ	Multidimensional personality questionnaire
MPRAGE	magnetization-prepared rapid gradient-echo
MRI	magnetic resonance imaging
mI	myo-inositol
NADPH	nicotinamide adenine dinucleotide phosphate
NEM	negative emotionality
NP	neuropsychological tests
PEM	positive emotionality
RFC	resting functional connectivity
RS	resting state
SA	Standard American diet
TLFB	Alcohol Timeline Follow-back
TS	task state
VAT	visual attention task
VBM	voxel-based morphometry

1. Introduction and Background

Effects of Alcohol on Brain Glucose and Acetate Metabolism

Alcohol is widely consumed; approximately 56% of Americans 18 years or older drink alcohol at least once a month [5]. Although the majority of individuals use alcohol in moderation, approximately 7.1% are heavy drinkers (5 or more drinks/day on at least 5 different days in the past 30 days) [6]. Thus, understanding the effects of heavy alcohol drinking on the human brain is crucial for developing interventions to minimize potential adverse effects.

Brain imaging studies have shown that acute alcohol administration decreases glucose metabolism in the human brain, which initially was thought to reflect decreased brain activity [7, 8, 9, 10]. However, subsequent studies showed that even low doses of alcohol and minimal behavioral effects also decreased baseline brain glucose metabolism [11], and that alcohol-induced reductions in brain glucose metabolism were significantly larger than those induced by benzodiazepines at doses that induced sedation [12]. Moreover in alcoholics the glucose metabolic decrements triggered by acute alcohol were significantly larger than those in controls even when the symptoms of intoxication were much lower than in controls [12]. This prompted us to hypothesize that the reduction in brain glucose metabolism during alcohol intoxication reflected the increased utilization by the brain of the alcohol metabolite acetate as an energy substrate. Specifically, acetate, which serves as an energy substrate for astrocytes [13], is readily taken up into the brain, and though its concentration in blood is normally low, it rises significantly during intoxication and this is enhanced in heavy alcohol users (see below).

Indeed using PET and $[^{11}\text{C}]$ acetate, we recently showed that during alcohol intoxication the brain increased metabolism of acetate while decreasing metabolism

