- At the discretion of the Principal Investigator (PI) and Medical Investigator, based on adverse event (AE) severity
- Non-compliance with protocol procedures or investigator request(s)
- Patient request

9. Outcome Measures

a. Primary outcome measures:

To assess ketogenic diet on:

1. Withdrawal ratings (CIWA) and Benzodiazepine use during withdrawal in the first week of detoxification.
2. Brain function (during rest and activation assessed with fMRI), neurochemistry (assessed with MRS) and structure (assessed with MRI).
3. NP performance.

b. Secondary outcome measures

To determine if ketogenic diet improves:

1. sleep.
2. mood.
3. alcohol craving.

10. Statistical Analysis

a. Analysis of data/ study outcomes

Withdrawal symptoms: We will use the CIWA-Ar to measure alcohol withdrawal, which will be measured daily [106, 107]. Because there are no studies on the KD on withdrawal symptoms we cannot predict the effect size to be expected. We will compare the scores on the CIWA-Ar between participants on the KD and participants on the control diet. Based on effects of medications used for treatment of withdrawal symptoms we expect a 30 % reduction in CIWA-Ar scores with KD [108].

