fMRI data will be analyzed using standard software such as statistical parametric mapping (SPM) software, AFNI, FSL, and/or in-house routines. For a standard fMRI analysis, all image volumes will be pre-processed to correct for inter-scan movement, and realigned within and between scans. Each subject's EPI images will be co-registered with the subject's own T1 anatomical images for individual analysis or co-registered to a template, generated by the population under study or a standard template. These co-registered images will also be normalized to a standard EPI template such as the Montreal Neurological Institute (MNI) reference brain for potential group analysis. Statistical analyses will be performed using fixed effects (for individual data), conjunctions analysis (between and/or within subjects), and random effects model (for group analysis such as gender differences). The fMRI signal change produced by a task will be estimated relative to baseline activation, or in comparison with other task. Resting state or steady state scans will also be analyzed using standard or in-house software and network analysis might be performed. Statistical contrasts of activation maps may be analyzed with within-subjects t-statistics. The analysis may include single individual cases, a group of participants with similar characteristics, or a comparison between males and females. Region of interest or whole brain analysis will be based on functional or anatomical landmarks. Data may be combined with other modalities and behavioral results.

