MRI data will be processed using adequate software such as SPM8, Freesurfer, Tortoise or DTI studio, to obtain, for each subject, images of gray and white matter, diffusion or perfusion maps. Images will then be compared using standard statistical parametric mapping software such as SPM, FSL, or AFNI, or even other more advanced programs as available. The statistical program will generate a group-specific adjusted mean value and an associated adjusted error variance for each voxel or region of interest that will be derived. Statistical significance may be established based on multiple-comparison corrections, permutations or simulations, in accordance with the analysis method selected. Data may be combined with other modalities and behavioral results. Accounting for multiple non-independent comparisons inherent in the analyses, a voxel level corrected P value < 0.05 will be used as the final threshold for significance. However, in line with functional imaging literature, results will also be reported as significant at a statistical threshold of $P < 0.001$, uncorrected, when a priori hypotheses require.

MRS data will be processed using specialized software packages such as LCModel, jMRUI or in house routines. These will be used to calculate ratios, such as GABA/Cr, NAA/Cr and, NAA/Cho. Anatomical images may be used to identify the ROI. Data may be combined with other modalities and behavioral results.

In case of group differences in severity of addiction or age due to randomization, we will add these variables as covariates to the analyses.

Plasma ghrelin

Weekly plasma ghrelin (total and acyl-ghrelin) will be analyzed using standard lab procedures [94]. Ghrelin levels will be compared between KD and SA group, and associated with weekly alcohol craving scores in both groups. We expect ghrelin to decrease in the KD versus SA group, and to be associated with the expected decreases in alcohol craving in KD.

b. Power analysis

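### The plan lets voxel results at uncorrected P < 0.001 be called significant for pre-stated hypotheses, so if the primary imaging Hypotheses 2–4 are tested voxelwise, error over the searched region is not controlled

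*Combined protocol and SAP*

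**What the plan says.** Section 9.a lists among the primary outcomes "Brain function (during rest and activation assessed with fMRI), neurochemistry (assessed with MRS) and structure (assessed with MRI").

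Section 10.a, in the paragraph on structural, diffusion and perfusion images, says "Images will then be compared using standard statistical parametric mapping software such as SPM, FSL, or AFNI". It describes an adjusted mean and an "adjusted error variance for each voxel or region of interest that will be derived". On thresholds, it first acknowledges the many dependent comparisons and states that "a voxel level corrected P value < 0.05 will be used as the final threshold for significance". The next sentence, appealing to practice in functional imaging, adds that "results will also be reported as significant at a statistical threshold of" P < 0.001, uncorrected, where a priori hypotheses call for it.

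The fMRI paragraph of the same section sets no threshold. It says "Statistical contrasts of activation maps may be analyzed with within-subjects t-statistics" and "Region of interest or whole brain analysis will be based on functional or anatomical landmarks".

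Section 10.b states Hypotheses 2–4 in advance: limbic response to alcohol cues, connectivity of the saliency network, and prefrontal atrophy with ventricular enlargement. They are to be tested by paired t-tests and, between diets, by mixed ANOVAs. With alpha 0.05, power 80% and 25 per arm, the section gives detectable effects of 0.66 and 0.9 respectively.

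**The concern.** The two threshold sentences give the same label to results of very different strength. The first controls error over the image. The second controls it only at each voxel, and it is reserved for the hypotheses that matter most. The condition for using it is not defined, and no mask, minimum cluster size or small-volume correction limits it.

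The reach of the clause differs by hypothesis. It sits in the structural paragraph, so it applies directly to the prefrontal part of Hypothesis 4 if that is tested voxelwise. Its reach to the fMRI Hypotheses 2 and 3 is an inference: their own paragraph has no threshold and allows contrasts of activation maps, and the clause cites the functional imaging literature.

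At stake is whether a chance voxel in a broadly named area (limbic, saliency network, prefrontal cortex) could be reported as a significant diet effect on a primary outcome. A reader also cannot tell which unit of analysis the alpha 0.05 power statement covers.

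**Working it through.** **1. The plan's own figures.** From Section 10.b: alpha 0.05 (taken as two-sided; the plan does not say), power 0.80, 25 per arm. Power is the probability that a noncentral t variable exceeds the critical t, with noncentrality

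- paired, within one arm: d × √n, with n − 1 df;
- between diets: d × √(n/2), with 2n − 2 df, where d is in SDs of change (an assumption, since the plan does not define the measure).

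| | Paired | Between diets |
|---|---|---|
| Plan's detectable effect | 0.66 | 0.9 |
| Detectable effect, n = 25 per arm | 0.584 | 0.809 |
| Detectable effect, n = 20 per arm | 0.660 | 0.909 |
| Power at the plan's effect, n = 25 per arm | 88.6% | 87.7% |

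If both arms are pooled (50 pairs), the paired figure is 0.404. The stated effects therefore fit about 20 per arm and are conservative for 25.

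These figures describe single tests at alpha 0.05. At two-sided 0.001, power for the same effects is 36% and 39%, so the power statement does not describe a test at the uncorrected voxel threshold.

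**2. Error over a region, independent elements.** With k independent tests at 0.001, the chance of at least one false positive is 1 − 0.999^k.

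- k = 51: 0.0497
- k = 52: 0.0507
- k = 100: 0.095
- k = 500: 0.394

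The rule holds 5% only up to 51 effective tests.

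**3. Error over a region, smooth images.** Neighbouring voxels are correlated, so smooth null fields were simulated. Everything here except the arm size is an assumption: 2 mm voxels; smoothness (FWHM) of 8, 10 and 12 mm; one between-diet contrast with 25 per arm (t field, 25 + 25 − 2 = 48 df); cubic regions of 7, 11 and 16 voxels per side. The volumes are 14³ mm³ = 2.7 mL, 22³ mm³ = 10.6 mL and 32³ mm³ = 32.8 mL. There were 10,000 runs per setting (4,000 for the largest region at 12 mm), with a Monte Carlo standard error of at most 0.007.

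Chance of at least one false result at uncorrected P < 0.001, for FWHM 8 / 10 / 12 mm:

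| Region | Any voxel, one-sided | Any voxel, two-sided | At least 10 contiguous voxels, one-sided |
|---|---|---|---|
| 2.7 mL | 0.066 / 0.041 / 0.032 | 0.079 / 0.045 / 0.035 | 0.011 / 0.010 / 0.012 |
| 10.6 mL | 0.202 / 0.134 / 0.089 | 0.233 / 0.156 / 0.104 | 0.042 / 0.047 / 0.037 |
| 32.8 mL | 0.471 / 0.323 / 0.215 | 0.524 / 0.366 / 0.248 | 0.126 / 0.124 / 0.095 |

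The two-sided column is the closer match to the plan: with two time points, the group-by-time F test in a mixed ANOVA equals a two-sided t-test on change.

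A separate simulation with 3 mm voxels, 8 mm FWHM and Gaussian fields shows the same pattern: 0.046 one-sided in 5³ voxels (15³ mm³ = 3.4 mL), 0.17 in 8³ (13.8 mL) and 0.46 in 12³ (46.7 mL).

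**4. After the change.** Correction within a named mask holds error for that map at 0.05. One summary value per measure is one test with no search. Neither handles the number of hypotheses: four independent tests at 0.05 (Hypothesis 4 has two measures) give 1 − 0.95⁴ = 0.185.

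**The case against.** The strongest reply is that Section 10.b points to a reading with no problem. A paired t-test or mixed ANOVA at alpha 0.05 with a single detectable effect suggests one summary value per hypothesis. Ventricular enlargement is naturally a volume, and Section 10.a names Freesurfer and allows region-of-interest values. On that reading the exception is never needed. This is a fair argument, but the plan does not say so, and the clause exists precisely to let a priori hypotheses use an uncorrected voxel threshold.

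The harm is also conditional. The test must be voxelwise, the region not small, and single voxels must count. In 2.7 mL the error is close to nominal, and with a 10-voxel extent rule it is about 1% to 5% in the two smaller regions. That stands. Lack of control here means that no procedure bounds the error, not that the error is always large.

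Two smaller points also stand. The listing of "voxel-based morphometry" in the abbreviations is weak evidence that Hypothesis 4 is voxelwise, because the methods never use the term; nothing here rests on it. And if a report prints the threshold beside the result, readers can discount it. That softens the harm but does not justify the label.

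A region named in advance is a good reason to correct over that region instead of the whole brain. It is not a reason to omit correction.

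**Conclusion.** The concern holds. The plan states a rule under which a result that fails its own final threshold may still be called significant, and nothing in the text limits that rule for the primary imaging hypotheses. It applies directly to the prefrontal part of Hypothesis 4 if tested voxelwise, and by inference to Hypotheses 2 and 3. It does not arise for any hypothesis tested on one pre-named value.

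The size depends on quantities that the documents do not give. Under the assumptions above, with any single voxel counted and a two-sided test, the false-positive chance runs from about 4% to 8% in a small region up to 25% to 52% in 32.8 mL. The plan should be changed on this point. Confidence is medium because the unit of analysis is unstated.

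The mismatch of 0.66 and 0.9 with 25 per arm is a separate, minor correction. It makes the study look slightly less sensitive than it is, and the main conclusion does not depend on it.

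**What to change.** 1. In Section 10.a, remove the word significant from the uncorrected clause. Suggested wording: *Results at P < 0.001 uncorrected will be reported as descriptive only.*
2. For each of Hypotheses 2–4, choose one of two routes before analysis. Either apply the existing corrected P < 0.05 rule within a mask named in advance, or test one pre-named summary value per measure (two for Hypothesis 4: prefrontal and ventricular).
3. In Section 10.b, state which of these the alpha 0.05 power statement covers.
4. Separately, restate 0.66 and 0.9 for 25 per arm (0.58 paired within one arm and 0.81 between diets, on the assumptions above), or give the sample size they assume.

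The cost is SAP wording plus the work of naming masks or summary values. No new data or design change is needed, and every voxel result can still be shown. The downside is that some voxel results lose the label significant. The change controls error within each hypothesis, not across them.

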We will collect DNA so that in the future when new findings emerge with respect to genes implicated in brain diseases so we can assess across integrated data from various brain imaging studies if they are associated with changes in brain connectivity. However, DNA collection will be optional and will not exclude subjects from participating in this study if they do not want to give blood for genotyping.

b. Data including genomic data and sample sharing plan

Samples and data, including genomic data may be shared with collaborators.

The following questionnaires/assessments/interviews collected under the 14-AA-0181 will be shared with this protocol: Smoking History Questionnaire [98]; Fagerström Test for Nicotine Dependence (FTND) [99]; The Timeline Follow-Back (TLFB) [100]; Alcohol Use Disorders Identification Test (AUDIT) [101]; Barratt's Impulsivity Scale (BIS-11) [102]; Structured Clinical Interview (SCID) for DSM-IV or DSM 5 [103]; Alcohol Dependence Scale (ADS) [104]; and Clinical Institute Withdrawal Assessment – Alcohol revised (CIWA-Ar) [105].

Data and samples may also be shared with collaborating laboratories at NIH or outside of NIH and/or submitted to NIH-designated repositories and databases if consent for sharing was obtained. Repositories receiving data and/or samples from this protocol may be open-access or restricted access.

Samples and data will be stripped of identifiers and may be coded (“de-identified”) or unlinked from an identifying code (“anonymized”). When coded data is shared, the key to the code will not be provided to collaborators, but will remain at NIH. Data and samples may be shared with investigators and institutions with an FWA or operating under the Declaration of Helsinki (DoH) and reported at the time of continuing review. Sharing with investigators without an FWA or not operating under the DoH will be submitted for prospective IRB approval. Submissions to NIH-sponsored or supported databases and repositories will be reported at the time of Continuing Review. Submission to non-NIH sponsored or supported databases and repositories will be submitted for prospective IRB approval.

Required approvals from the collaborating institution will be obtained and materials will be shipped in accordance with NIH and federal regulations.

6. Additional Considerations

a. Research with investigational drugs or devices

N/A

7. Risks and Discomforts

Potential risks from this study include the following:

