Empirical knowledge regarding the necessary sample size for significant effects of a ketogenic diet on withdrawal, NP or brain functioning in AUD during withdrawal does not exist. Previous behavioral and pharmacological treatment studies in AUD with behavioral, fMRI and MRS as outcome measures have studied on average 20-25 patients per group [treatment versus control: reviewed in 109]. Clinical efficacy of a ketogenic diet in epilepsy was established in randomized-controlled trials in 20 [55] or 94 epilepsy patients [56]. In 20 elderly participants, an acute dose of ketogenic meal improved executive functioning 1.5-3 hours after, as compared to a control meal on a different day [58]. Further, beneficial effects of KD on sleep was established in a study in 18 children with epilepsy [57]. Thus, for within-subject fMRI studies in individuals with AUD sample sizes of 25 patients per group have been effective for obtaining interpretable data regarding behavioral and neurocognitive effects of treatment, suggesting that the sample size of the current protocol is adequate for the identification of effects of ketogenic diet in AUD.

Independent sample t-test will be used to test **Hypothesis 1**, “withdrawal symptom severity within the first week of detoxification will be lower for patients with KD compared to control diet”.

Paired t-test on BOLD signals will be used to test **Hypothesis 2**, “limbic activation to alcohol cues would be reduced after 3 weeks of treatment”; **Hypothesis 3**, “the functional connectivity of the saliency network will be stronger after 3 weeks of treatment”; **Hypothesis 4**, ‘prefrontal cortex atrophy and ventricular enlargement will stronger decrease after 3 weeks of KD treatment compared to control diet’. Assuming a threshold probability for rejecting the null hypothesis (Type I error rate), $\alpha = 0.05$, and a probability of failing to reject the null hypothesis under the alternative hypothesis (Type II error rate), $\beta = 0.2$, the

proposed sample sizes (25 KD versus 25 ND) will allow us to detect an effect size of 0.66.

To test KD treatment effects, mixed ANOVAs will be used to assess whether KD group shows reduced brain activation (Hypothesis 2), higher functional connectivity (Hypothesis 3), and prefrontal cortex atrophy and ventricular enlargement (Hypothesis 4) compared to the control diet group. Assuming $\alpha = 0.05$ and $\beta = 0.2$, the proposed sample sizes will allow us to detect an effect size of 0.9.

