Pearson correlation will be used to test **Hypothesis 5**, “acetone and β -hydroxybutyrate concentration in the anterior cingulate and frontal white matter will increase linearly as a function of time week #1, #2 and #3”. Assuming $\alpha = 0.05$ and $\beta = 0.2$, the proposed sample sizes will allow us to detect statistically significant correlation coefficients, $r > 0.6$.

From our past experience with neuroimaging of patients with AUD, it is expected that, even with careful screening and preparation, approximately 50% of participants will not be able to complete protocols with neuroimaging like the current one being proposed. Thus, we are proposing to recruit 100 participants in order to complete studies in 50 of them (25 on KD and 25 on SA diet).

* We expect that more than 25 patients per group will finish the first week of KD and its assessment of withdrawal symptoms, and will therefore include all patients who finished these assessments to test Hypothesis 1.

11. Human Subjects Protection

a. Subject selection

Adults who fulfill the eligibility criteria will be included, regardless of race, ethnicity, sex, or religious affiliation. We predict the racial composition is approximately 60% Caucasian, 35% African American, and remaining 5% proportion of Asian or other. We predict the Hispanic ethnicity to be approximately 25%. On the same basis, the expected breakdown is 70% male and 30% female. The age range of 18 years and older will provide a sample size that hits our target inclusion criteria of a minimum of 5 year of heavy drinking history.

b. Justification for exclusion of children

Children are excluded since it is unlikely that they will meet the ten-year criteria of heavy drinking required for the study.

c. Justification for exclusion of other vulnerable subjects

Vulnerable populations such as those who lack capacity to consent, are also excluded due to the likely inability to follow instructions for tasks to be performed during diet (KD or SA meal/shake protocol) randomization, MR scans and NP

testing. We also exclude individuals with major psychiatric disorders since this may affect brain function and structure, and may influence study results.

d. Justification for sensitive procedures

N/A

e. Safeguards for vulnerable populations and sensitive procedures

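### Section 10.a adjusts for age and addiction severity only if the arms turn out to differ, which leaves the KD-SA models for Hypotheses 2-4 open until the data are seen and may waste precision

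*Combined protocol and SAP*

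**What the plan says.** The only covariate rule is in Section 10.a: "In case of group differences in severity of addiction or age due to randomization, we will add these variables as covariates to the analyses". The sentence does not say how a difference is to be judged (a test, a threshold or inspection) or which measure stands for severity. Section 5.b lists the Alcohol Dependence Scale, the AUDIT and the Timeline Follow-Back among the instruments shared from 14-AA-0181. Age is available from the screening demographics (Section 4.d).

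Nothing elsewhere overrides the rule. For the between-arm part of Hypotheses 2-4, Section 10.b says "To test KD treatment effects, mixed ANOVAs will be used to assess whether KD group shows reduced brain activation" and likewise for connectivity and structure, with no covariate named. For Hypothesis 1 it says "Independent sample t-test will be used to test" withdrawal severity, again unadjusted. Section 10.a also mentions adjusted means for voxels or regions, but only as output of the imaging software, without naming covariates. Section 4.e.2 does not describe randomization as stratified by age or severity.

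**The concern.** Adjusting for a baseline variable is worthwhile when that variable predicts the outcome. The size of the difference between two randomized arms carries no information on that. A rule triggered by imbalance therefore drops a strong predictor when the arms look alike and may add a useless one when they do not.

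Two things are at stake:

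- **An undecided model.** Whether the arms differ, and on which severity scale, is settled after the data exist. Section 4.e has the individual blind broken participant by participant after the final MRI, so the judgement is not protected from knowledge of allocation and results.
- **Precision.** With 25 per arm there is little to spare. The protocol gives some reason to expect prediction: its background section reports that cue reactivity, the Hypothesis 2 outcome, has been linked to clinical severity. Eligibility is also wide on both variables: adults with no upper age limit, and DSM-IV abuse or dependence or DSM 5 moderate or severe AUD.

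**Working it through.** **Inputs.** From Section 10.b: 25 per arm, α=0.05, power 0.80, and the stated effect sizes 0.66 and 0.9. Assumed, because the documents do not say: two-sided tests, effect sizes read as Cohen's d, a trigger of P<0.05 or P<0.20 on each covariate, two independent covariates, and a joint R² between 0 and 0.3.

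**1. The plan's own figures.** For the mixed ANOVAs the plan states: "Assuming $\alpha = 0.05$ and $\beta = 0.2$, the proposed sample sizes will allow us to detect an effect size of 0.9". After the paired tests it states that the "proposed sample sizes (25 KD versus 25 ND) will allow us to detect an effect size of 0.66". For an unadjusted two-sample comparison, the noncentrality is d × √(25/2) = 3.536d on 48 df. That gives 80% power at d=0.81, not 0.9. A paired test with 25 gives 0.58, not 0.66. Both stated figures fit 20 per group instead (0.91 and 0.66). This is a separate matter. Here 0.66 and 0.9 serve only as reference effects, at which unadjusted between-arm power with 25 v 25 is 0.628 and 0.877.

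**2. How often the covariates would be used.** P(at least one triggers) = 1 − (1 − p)².
- p=0.05: 1 − 0.95² = 9.75%, so about 90% of trials use neither covariate.
- p=0.20: 1 − 0.80² = 36%, so 64% use neither.
- Most trials stay unadjusted until p reaches 1 − √0.5 = 0.29.

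**3. Power.** Always adjusting for two covariates leaves 46 df and a noncentrality of d/√(1 − R²) × √(12.5 × (1 − 2/48)) = 3.461d/√(1 − R²). At d=0.66 this is 2.284 for R²=0, against 2.333 unadjusted, and 2.730 for R²=0.3. The d=0.66 columns below come from simulation (60,000 trials per setting, trigger P<0.05). The formula gives 61%, 65%, 71% and 76% for always adjusting. The last two columns are from the formula.

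| Assumed R² | Conditional, d=0.66 | Always, d=0.66 | Always, detectable d at 80% | Always, power at d=0.9 |
|---|---|---|---|---|
| 0 | 62% | 61% | 0.83 | 0.862 |
| 0.1 | 63% | 65% | 0.78 | 0.895 |
| 0.2 | 63% | 70% | 0.74 | 0.926 |
| 0.3 | 63% | 76% | 0.69 | 0.954 |

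The unadjusted comparators for the last two columns are 0.81 and 0.877. Break-even is where (1 − 2/48)/(1 − R²) = 1, that is R² = 2/48 = 0.042. The two lost degrees of freedom push it up slightly, to 0.04-0.05.

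**4. Type I error.** For R² from 0 to 0.5, the conditional rule rejects a true null in 3.6-5.1% of trials with the P<0.05 trigger and 2.5-5.0% with P<0.20. If an analyst instead took the smallest P among the four possible covariate sets, it would be 6.2-11.1%.

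**5. Group-by-time tests.** With two time points, the group-by-time test is the two-sample comparison of change. Age and baseline severity are constant within a participant, so what they explain of a participant's level cancels. Only their R² with change enters the table. With complete data, covariates entered as main effects alone leave this test essentially as it was. They must be crossed with time to help.

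**The case against.** The strongest reply is that the gain is unproven where it matters. The planned KD-SA tests for Hypotheses 2-4 are mixed ANOVAs over repeated scans. The documents give no R² with change over about three weeks, and it may be near zero. In that case always adjusting costs 1-2 points: at d=0.81, 0.801 unadjusted falls to 0.783. This stands. It limits the claim about power, but does not supply a reason to choose covariates by imbalance.

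The rule also names its two variables in advance and looks at baseline data, not outcomes. That is true, and it narrows the analyst's freedom. The trigger and the scale remain open.

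A reader might infer that the rule inflates false positives. Applied mechanically it does not: its error rate is nominal or slightly below. The 6.2-11.1% in the working needs deliberate selection of the best result, and nothing in the documents says that is intended.

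A reader might also infer that all primary imaging, MRS and NP models are affected. The documents write no between-arm MRS model (Hypothesis 5 is a correlation with time) and no NP model at all. NP is primary in Section 9.a but secondary in the précis and Section 2.b. The point therefore attaches to Hypotheses 2-4, and to other between-arm comparisons only if they are made.

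Lastly, the 10% trigger rate assumes chance imbalance. About half of participants are expected not to complete, and removal for negative urine ketones applies only to KD (Section 4.e.3). Imbalance among completers need not be chance, so the trigger could fire more often. It is also unclear whether such a difference would count as arising from randomization. This weakens the 10% figure but strengthens the case for fixing covariates in advance.

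**Conclusion.** The concern holds in a limited form. Section 10.a lets observed imbalance decide whether age and severity enter the KD-SA models of Hypotheses 2-4, with neither trigger nor scale defined. Under a test-based trigger at P<0.05 or P<0.20, most trials would use neither covariate.

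At d=0.66, always adjusting changes power by about −1 point at R²=0 and by about +2, +7 and +13 points at R² of 0.1, 0.2 and 0.3. These figures rest on an assumed R², 25 v 25 completers, two-sided 0.05 and independent covariates. For change outcomes the true value may lie at the low end. That precision is lost is therefore conditional; that the model is left open is not. This is a cheap improvement to the plan, not a flaw that invalidates the trial.

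**What to change.** Replace the sentence in Section 10.a with:

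> Each KD-SA comparison in Hypotheses 2-4, and any other between-arm imaging, MRS or NP comparison that is made, includes age and one severity score named in advance (for example ADS total) as covariates, entered with their time interactions in repeated-measures models, whatever the observed balance. The unadjusted result is a sensitivity analysis. Baseline differences are not used to choose covariates.

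ADS is only an example. AUDIT or a TLFB summary would serve equally, provided one is fixed before the data are examined.

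The cost is one sentence, no new data and two of 48 error degrees of freedom. If the covariates explain almost none of the outcome or its change, about 1-2 points of power are lost.
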